After randomization, the 40 participants assigned to the psilocybin condition will receive specialized preparation for their psilocybin session in treatment meetings 3 and 4. They will then be administered 30mg/70kg psilocybin on their mutually agreed upon Target Quit Date (TQD) in approximately week 5. These participants will meet with study staff the day after their psilocybin session for debriefing, and 25 of these will additionally complete a 4-6 hour post-psilocybin MRI scan that day. Treatment meetings will continue weekly for two weeks after the psilocybin session, and at 2-week intervals from weeks 9 through 13 to discuss the session experience and to provide support for smoking cessation. Participant smoking status will be assessed repeatedly at five meetings after the psilocybin session using self-report and breath carbon monoxide (CO) samples. Smoking status will also be assessed at three follow up meetings approximately 3, 6, and 12 months after the psilocybin session using self-report, breath, and urine samples. All study meetings will have the option to be completed remotely using a secure online format, including remote breath CO monitoring and mailed in or at home urine sample tests, with the exception of physical examination during initial screening, psilocybin sessions, and MRI scan procedures.

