#### All standard study meetings, meeting content, and duration are summarized here:

\* Indicates MRI procedures to be completed only by participants who are eligible for MRI scanning (n=60).

a Times listed in the table are approximate.

bMRI Scan 4 only for participants showing biologically verified abstinence at 3-month follow-up.

Intentions and expectations for the psilocybin session will be discussed. Furthermore, a structured cognitive-behavioral smoking cessation intervention will be implemented throughout the course of these meetings to prepare participants for smoking abstinence and potential withdrawal. Throughout the preparatory meetings, participants will be encouraged to view the psilocybin session as providing an opportunity for deep reflection about the role of smoking in their lives. The purpose of the psilocybin session is to enhance motivation for initiating a quit attempt. Procedures for drug administration and the conduct of the session will be similar to

procedures used in our previous (Griffiths et al., 2006, 2008, 2011) and ongoing studies with psilocybin (IRB # NA\_00001390 in cancer patients; IRB # NA\_00020767 in healthy adults), and are described below in the section "Conduct of Psilocybin Sessions."

Participants will meet with study staff for debriefing one or two days after the psilocybin session. Participants will then meet weekly with study staff for 2 weeks after their psilocybin session (i.e., in weeks 6 and 7), and at 2-week intervals until the end of the 13-week study treatment (i.e., in weeks 9, 11, and 13). The general purpose of the meetings following the session is to provide a context for discussing and integrating experiences from the psilocybin session, and to provide support for smoking cessation. Additional contact hours will be scheduled if it is judged that the participant would benefit from further meetings with study staff to discuss experiences from the session or provide additional support for smoking abstinence. Aside from the psilocybin session and MRI scan visits (if applicable), all meetings may be held remotely using a secure online platform, including use of remote CO monitoring and mailed in or at home urine sample testing.

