Meetings Before and After TQD (NRT Condition): Before the target-quit date participants in the NRT condition will meet with one or more of the study staff on at least 3 occasions, for a minimum of 4 hours of contact time before drug administration. Some flexibility in scheduling will be allowed to account for unexpected absences such as travel commitments or illnesses. The main purpose of the participant-staff meetings is to prepare participants for NRT transdermal patch administration, and to deliver a cognitive-behavioral smoking cessation intervention identical to that received by participants in the psilocybin condition. During these meetings study staff will answer any questions related to NRT, examine motivations to quit smoking, and encourage preparation for smoking cessation on the target-quit date. Participants in this condition will be provided with NRT patches and instructed how to use the patches, which may be mailed to participants to reduce unnecessary in-person visits. In week 5, participants in the NRT condition will begin a standard 8 to 10 week course of NRT for smoking cessation. For MRI participating volunteers, nicotine patches will be initiated directly after their week 5 MRI scan. All participants in the NRT condition will have five additional counseling meetings with study staff in weeks 6, 7, 9, 11, and 13, where they will provide self-report and breath samples to assess smoking status and complete study questionnaires. The study physician will be available during the study to discuss any potential side effects or medical issues. Participants will complete questionnaires and provide breath and urine samples to evaluate smoking status at approximately 3, 6, and 12 months post-TQD.

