NRT Condition: Participants in the NRT condition will receive preparation and instructions from study staff on how to use the nicotine transdermal patch, which may be mailed to them to reduce in-person contact. Participants will receive detailed information on NRT and potential side effects prior to patch administration. On the day after their Target-Quit Date in week 5, they will be provided with a 2-week supply of medication, and instructed to begin a standard 8 to 10 week transdermal nicotine patch regimen according to recommended label usage (For individuals who smoke more than 10 cigarettes per day: 21mg daily for weeks 1-6, 14mg daily for weeks 7-8, 7mg daily for weeks 9-10. For individuals who smoke 10 or less cigarettes per day: 14mg daily for weeks 1-6, 7mg daily for weeks 7-8; FDA label, PDR.net). For MRI participating volunteers receiving NRT (n=25), the Target-Quit Date will occur 24 hours prior to the MRI scanning day in week 5, and participants will begin using NRT immediately after that MRI scan is completed. To ensure matching treatment procedures, participants randomized to the NRT condition who are not MRI participating volunteers, and are completing only the treatment portion of the protocol (n=15), will also stop smoking 24 hours prior to their meeting in week 5 (to be confirmed by breath CO). At this meeting they will receive their first 2-week supply of transdermal nicotine patches and initiate NRT use. Participants will receive additional supplies of appropriate dose patches at 2-week intervals around their regularly scheduled treatment meetings. Participants will be asked to notify study staff immediately in case of adverse events or side effects, and will determine with the study physician whether NRT dosage should be adjusted, or permanently discontinued. In the unlikely event of a severe side effect such as a myocardial infarction/arrhythmia, participants will be advised to immediately discontinue NRT use. Under these circumstances, participants will be asked to continue the study protocol meetings to completion.

After completing the 6-month follow-up, participants initially randomized to the NRT condition will be eligible to undergo an optional high-dose (30mg/70kg) psilocybin session. If they choose to take part, they will receive two weekly preparation meetings, one high-dose

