*Persisting Effects Questionnaire:* This 145-item questionnaire was designed to measure changes in attitudes, moods, behavior, and spiritual experience, and has demonstrated sensitivity to the intermediate and long-term effects of psilocybin (Griffiths et al., 2006, 2011). The questionnaire has been modified for this study to additionally assess attributions volunteers make retrospectively to their treatment experience, and how it may have facilitated smoking cessation.

*Monitor Rating of Enduring Effects:* This questionnaire will assess the monitor's observations of persisting effects of study participation on participant attitudes and behaviors.

*States of Consciousness Retrospective Questionnaire*: This questionnaire has been used in our previous psilocybin research (Griffiths et al., 2006) for purposes of long-term follow-up. Some items on this questionnaire comprise the States of Consciousness Questionnaire, and are completed retrospectively for the experience. Other items comprise the previously described Persisting Effects Questionnaire. For these items, volunteers are asked to rate any current persisting effects that they attribute to the experience. Within the Retrospective Questionnaire, volunteers are also asked to provide written descriptions of what was most memorable and what was most spiritually significant about the experience.

*Adverse Events Form:* After TQD participants will be asked at each study treatment meeting to report on how they have been feeling since their last in-person meeting. In the case of any adverse events (AEs), these will be documented using an AE form, which assesses the nature of

AE, duration, severity, and what course of action was taken to address the event.

**COVID-19 Protocol Feedback:** At the end of treatment (~8 weeks after TQD) participants will be asked to complete a brief questionnaire designed by our team to assess the perceived impact of COVID-19 related study procedures (e.g., mandatory COVID-19 testing, masks / PPE, virtual meetings) on key elements of their study experience (e.g., psilocybin session, relationship with study team, quit attempt, sense of safety).

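### Adverse events are asked about since the last in-person meeting although most meetings may be remote, so recall windows can overlap and can differ between arms

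*Combined protocol and SAP*

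**What the plan says.** Section 6.b describes the AE form among the secondary outcome variables: "After TQD participants will be asked at each study treatment meeting to report on how they have been feeling since their last in-person meeting". As summarised there, the form covers the nature of an event, its duration, its severity and the action taken. The summary mentions neither an onset date nor how a repeated report is handled.

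Section 3.a (Study design) states: "All study meetings will have the option to be completed remotely using a secure online format", "with the exception of physical examination during initial screening, psilocybin sessions, and MRI scan procedures". The text on meetings in the psilocybin condition repeats this: "Aside from the psilocybin session and MRI scan visits (if applicable), all meetings may be held remotely using a secure online platform". For the NRT condition, section 3.a says of the patches: "which may be mailed to participants to reduce unnecessary in-person visits".

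The last obligatory in-person contact differs by group. The psilocybin session is always in person and falls on the TQD, in about week 5. In the NRT arm, section 3.a (NRT Condition) says: "For MRI participating volunteers receiving NRT (n=25), the Target-Quit Date will occur 24 hours prior to the MRI scanning day in week 5", and patch use begins straight after that scan. The remaining 15 NRT participants complete treatment only. The blood draw one week after TQD, which needs a visit, is optional (section 6.b).

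Section 6.c names no AE comparison between arms. Sections 6.d and 7.c describe safety monitoring and reporting to the IRB.

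**The concern.** An AE question that restarts at the last in-person meeting works if people attend in person. Under the remote option it does not restart, so each remote meeting asks again about weeks already covered.

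The starting point also differs by arm. A psilocybin participant's window cannot begin before treatment. An NRT participant outside the MRI subset who attends remotely can be asked in week 13 about everything since screening. The weeks before the TQD are not empty: participants agree to abstain for 24 hours before the week 2 visit (section 4), and withdrawal symptoms such as nausea and sleep disturbance (section 7.a) resemble listed patch effects. Unless onset is recorded, a symptom from before the first patch could be tabulated as if it followed treatment. What is at stake is whether AE counts by arm in this unblinded trial cover the same period.

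**Working it through.** The plan gives no AE rate, no share of meetings held remotely and no figure to reproduce. The check counts recall weeks from the visit schedule.

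Inputs:
- Meetings after treatment start: section 3.a gives the NRT arm "five additional counseling meetings with study staff in weeks 6, 7, 9, 11, and 13", and the same weeks apply in the psilocybin arm.
- Treatment start: week 5 in both arms (section 3.a).
- Last obligatory in-person contact: the session (psilocybin), the week 5 scan (NRT with MRI), or screening (NRT without MRI).
- Screening at week 0 or week 1: an assumption. The schedule places it before week 1 without a date.
- NRT participants without MRI: 15/40 = 37.5% (section 3.a). The abstract instead has 100 randomised, 60 scanned and 40 not. An equal split of the 40, which is an assumption, gives 20/50 = 40%.

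Window at each meeting = meeting week − week of last in-person contact.

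| Case | Windows at weeks 6, 7, 9, 11, 13 | Sum | Distinct weeks |
|---|---|---|---|
| All in person, either arm | 1, 1, 2, 2, 2 | 8 | 8 |
| All remote, contact in week 5 (psilocybin; NRT with MRI) | 1, 2, 4, 6, 8 | 21 | 8 |
| All remote, screening at week 0 (NRT without MRI) | 6, 7, 9, 11, 13 | 46 | 13 |
| All remote, screening at week 1 (NRT without MRI) | 5, 6, 8, 10, 12 | 41 | 12 |

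Overlap with a week 5 contact: 21/8 = 2.6, so each week is asked about 2.6 times on average. Pre-treatment part in NRT without MRI: 5 meetings × 5 weeks = 25 of 46 (54%), or 5 × 4 = 20 of 41 (49%).

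Average distinct weeks over the whole NRT arm, against 8 for psilocybin:
- 40 per arm, screening at week 0: (25×8 + 15×13)/40 = 9.9; ratio 1.23.
- 50 per arm, screening at week 0: (30×8 + 20×13)/50 = 10.0; ratio 1.25.
- Screening at week 1: (25×8 + 15×12)/40 = 9.5, ratio 1.19; (30×8 + 20×12)/50 = 9.6, ratio 1.20.

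Each further week between screening and week 0 would add 15/40 = 0.375 (or 20/50 = 0.4) weeks to the NRT average, about 0.05 to the ratio.

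If every window were recorded afresh, the ratio of summed weeks would be (25×21 + 15×46)/40 = 30.4 against 21, or 1.45, and (30×21 + 20×46)/50 = 31.0 against 21, or 1.48. With screening at week 1 it would be 28.5/21 = 1.36 and 29.0/21 = 1.38.

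Meeting 5, in week 5, is outside these counts. The psilocybin meeting follows the session by a day and looks back to it. The NRT meeting coincides with patch start, so its look-back lies before the first patch even with in-person attendance.

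**The case against.** The strongest reply is that no between-arm AE analysis is planned. Section 6.c names smoking urges and withdrawal as its examples, and safety data are otherwise for monitoring and IRB reporting. This stands in part. The AE form is listed under secondary outcomes and the examples in 6.c are not exclusive, but the most that can be said is that a descriptive table by arm could be affected.

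Second, other routes catch events. Section 3.a (Monitor Telephone Contact) provides a daily call or text in both arms for the first seven days after TQD, NRT participants are asked to report AEs at once, and a headache interview follows each psilocybin session. These limit the recall problem just after TQD. They do not supply onset dates or a rule for repeats.

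Third, the form itself is not in the documents and may carry dates. That is why the fix asks the team to make sure that it does.

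A reader might infer three stronger things. One is that NRT counts would be 13/8 = 1.6 times too high, a false rate ratio of 8/13 = 0.62 in favour of psilocybin. That applies only to NRT participants without MRI. The others have an in-person scan immediately before the first patch. It also assumes a constant AE rate, whereas section 7.a expects withdrawal symptoms to peak in the first week after quitting. Another is that psilocybin would necessarily look safer. Forgetting over a longer window could lower NRT counts instead. The third is that overlapping windows double-count events. Asking twice is not recording twice, and nothing in the documents shows that staff would do so.

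**Conclusion.** The wording conflicts with the remote-visit provisions, and this is a minor but real defect. Followed literally, it makes recall windows overlap in both arms. At weeks 6 to 13 it lets them reach back before treatment for NRT participants without MRI (37.5% to 40% of that arm) and for nobody in the psilocybin arm.

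The arm-level difference is 9.9 to 10 weeks against 8, a ratio of about 1.2. This is an upper-end figure: it assumes that every optional meeting is remote, that the wording is applied literally and that screening falls at week 0. Reading it as a ratio of AE counts also needs a constant AE rate, which section 7.a does not support. At weeks 6 to 13 there is no difference if meetings are held in person. The remote share is not given, so the actual effect is unknown and its direction is not certain. The primary outcome is untouched.

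**What to change.** In section 6.b (Adverse Events Form), ask about the time since the last study meeting, in person or remote, and at the first meeting after TQD ask about the time since TQD. Use the same wording in both arms and at the meetings after an optional psilocybin session. With this rule the weeks 6 to 13 windows are 1, 1, 2, 2 and 2 weeks, 8 in total, in both arms, and the look-back at NRT meeting 5 is limited to the day since TQD.

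Make sure the form records onset date, and record a continuing event once. When tabulating by arm, list events with onset before first treatment (psilocybin session or first patch) separately and do not discard them. A cut-off at TQD would not do, because it would drop events from earlier study procedures such as the week 2 MRI, and in the NRT arm TQD falls 24 hours before the first patch.

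The cost is one sentence and one date field, with no added visits.

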#### Functional Neuroimaging (fMRI; for MRI participating volunteers only):

Smoking cessation and withdrawal have been well documented to affect brain function, including resting state functional connectivity, and smoking related cue-reactivity (McLernon et al., 2007; Sutherland et al., 2012). In order to examine the underlying neurobiological mechanisms associated with psilocybin-facilitated smoking cessation, and identify potential brain based mediating factors predictive of treatment outcomes, up to 60 participants will undergo two to three brain scans collecting fMRI data while performing the tasks detailed below. The first scanning session will take place in week 2 of treatment, after a 24-hour period of smoking abstinence. The second will occur in approximately week 5 of treatment (i.e., one day after the psilocybin session, or immediately before initiating NRT), after another 24-hour period of smoking abstinence. Participants who provide biologically verified (i.e., breath CO), and selfreport seven-day point prevalence abstinence at 3 months post-TQD will receive a final followup MRI scan at that time. Functional neuroimaging will be conducted at NIDA IRP by trained MRI operators under the supervision of [name]. In addition to these scanning sessions, MRI participating volunteers will also be given the option to participate in a preliminary MRI scan through a NIDA-approved sub-study protocol. Either the primary study scans or the preliminary study scan will include a clinical scan to be examined for incidental findings.

State of the art, multimodal imaging will be performed on a Siemens 3T Trio scanner, located at the NIDA-IRP (intramural research program). Participants' heads will be placed inside the RF coil and held in place by a head restraint that generally consists of soft foam padding. For most scanning experiments, a blipped, gradient-echo, echo-planar image (EPI) pulse sequence (e.g. TE = 27ms) is used with a TR of about 2 seconds. Specific imaging parameters (e.g. number of slices, slice angle, TR, TE, flip angle etc.) may be changed in order to maximize signal integrity. A "watchdog" program runs continuously on the MRI computer during all pulse sequences and ensures that no scanning parameter ever exceeds FDA guidelines.

*Resting Scan.* An EPI scan to assess resting-state fluctuations (RSF) will be conducted. These scans will provide us with information relating to trait and perhaps state connectivity between different prefrontal and limbic brain regions. Completion time: ~10 min.

*Multisource Interference Task (MSIT):* The MSIT is a cognitive control task that reliably and robustly activates the anterior cingulate cortex and fronto-parietal executive control and attention network (Bush & Shin, 2006). During each trial participants view three numbers (e.g., 2 1 1) and are required to identify the "oddball" number which differs from the other two (i.e., 2) as quickly as possible by pressing the corresponding number on a 3 button response box (1, 2, 3). On some trials the location of the oddball is the same as the location on the response box (e.g., 2 2 3) and sometimes it is different (e.g., 2 1 1). This latter trial type produces a slowing in response time that reflects conflict produced by flanker stimuli and the need to respond to stimulus identity (i.e., press 2) and suppress the response to stimulus order (i.e., press 1). Completion time 15min.

*Cue-elicited Craving:* Participants are presented two kinds of stimuli, smoking-related picture cues and neutral pictures (see Fig. 1). The smoking-related pictures are selected from Mucha's study (Mucha et al., 1999) and the International Smoking Image Series (Gilbert and Rabinovich, 1999) and similar smoking and neutral images from open source internet sites. The content of neutral cues are paired to smoking-related cues, but eliminate any smoking-related information.

Smoking-related

Neutral

#### Fig. 1: Sample stimuli. One representative pair is showed above.

*Structural Images:* A set of high resolution structural MR images will be collected. The images will be acquired using a T1-weighed three-dimensional MPRAGE sequence and will be used for the display of functional data. Completion time: ~5 min.

*Amygdala Reactivity Task:* Participants will complete a simple perceptual task previously shown to produce robust bilateral amygdala activity (Pezawas et al., 2005; Hariri et al., 2002; Foland-Ross et al., 2010), as well as top-down prefrontal regulation of amygdala reactivity (Hariri et al., 2002; Foland-Ross et al., 2010). This blocked fMRI paradigm consists of two experimental conditions: a face matching condition, and a sensorimotor control condition. During the emotion matching condition, participants view an array of 3 faces and their task is to select (via button press) one of the two faces that matches the identity of the target face. During the sensorimotor control task, participants view an array of 3 geometric shapes (circles, vertical and horizontal ellipses) and select one of the two shapes (bottom) that matches the target shape (top). Each block begins with a brief instruction screen ("match face" or "match shape"). During each emotion block different images selected from a standard set of pictures of facial affect (Lang et al., 2001), are presented. During the control blocks, different geometric shapes are presented in a pseudo-random order. Completion time: ~7min

*Central executive function of attentional switching within verbal working memory task:* Our previous work (Garavan et al, 2000) revealed widespread activation associated with attention switching within working memory (WM). Subjects will perform a verbal WM counting task. In each trial, subjects will be presented with a series of large and small squares and, using a response device, must report final counts at the end of each trial. The order in which the squares are presented dictates whether an update of the same count is required (e.g., two large squares in succession requires two updates of the "large square" count) or whether subjects must switch attentional focus to update the "other" count (e.g., a large square followed by a small square requires an update of the "large square" count followed by a switch to the "small square" count and an update of it). A parametric manipulation will produce trials with different numbers of switches, thus, for each particular trial length there will be a LOW, MEDIUM, and HIGH switching density trials ~ 10 min.

*N*-back task: The n-back visual working memory task (Kane et al., 2007) will be administered to assess working-memory performance. During the n-back task participants are presented with a series of single letters in a pseudorandom order and are required to decide whether the current stimulus matches that which appeared n items previously (Kane et al., 2007). ~20min

**Dot Probe Task:** A dot-probe task will be administered outside of the MRI scanner to assess for attentional bias to smoking-related stimuli (Ehrman et al., 2002). Each trial of the task begins with a fixation cross followed by a brief (~500ms) presentation of two images, one smoking-related and one neutral image either side of the fixation cross. Immediately after the offset of these images a target (dot probe) appears either in the position where the smoking-related image was, or where the neutral image was. Participants are required to respond as quickly as possible to the dot probe and the latency to respond provides a behavioral measure of how much attention was directed to either the preceding smoking-related images, responding will be faster on trials where the probe appears behind the smoking-related image and slower on trials where the probe appears behind the neutral image. Completion time: ~5min

